Assessment of the effect of treatment will be based on a non-randomized, open-labeled, prospective study of intravenously administered Omegaven[®] fat emulsion to determine safety and preliminary efficacy in the treatment of PN associated liver injury. This treatment group will be compared to a group based on historical controls, i.e., a subset of patients (those whose direct bilirubin levels was ever > 2 mg/dL) previously studied by Andorsky et al.(31) This study included neonates treated between 1986 and 1996 who depended on parenteral nutrition for at least 90 days after surgical therapy for congenital or acquired intestinal diseases. Our study will primarily follow the patients included in Andorsky et al. study from 2 months before direct bilirubin first reached a level > 2 mg/dL (baseline date) until 2 months after patients either reached 3 consecutive bilirubin levels \leq 2 mg/dL or reached one bilirubin level \leq 2 mg/dL and were weaned from PN died, or underwent a liver transplant. In our exploratory analyses, we will include the entire available follow-up time in Andorsky et al. dataset for each patient.

b. Patient Selection and Inclusion/Exclusion Criteria

Omega-3 Fat Emulsion (Omegaven[®])

After the diagnosis of PNALD is made, patients who are followed by the Clinical Nutrition Service (CNS) or General Surgery Program, in conjunction with the patient's primary physician, will contact [name] or [name] and an evaluation will be performed. Cases may also include referrals of patients with PNALD from other healthcare facilities or self-referrals. If the patient's parents or guardians agree to participate in the study, informed consent will be obtained. The history of present illness and past medical history will be reviewed with the guardian and pertinent demographic and medical information will be recorded on data collection forms. This form will be used to record all laboratory results, nutritional history, and descriptions of any liver biopsies performed.

Though most patients receiving parenteral nutrition do not develop end stage liver disease, there is a small percentage of patients, typically infants and children on prolonged courses of parenteral nutrition, who do go on to develop fulminate liver failure. The study population of this protocol is limited to patients felt to fulfill any one of the following conditions:

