As previously mentioned, Omegaven® may be infused in the same manner as conventional fat emulsions through either a central or peripheral line. The emulsion is isotonic. It is compatible with parenteral nutrition solutions and may be co-infused via y-site. Per Infection Control, source containers must be changed every 12 hours and unused product discarded. Omegaven® may be infused through a 1.2micron inline filter.

Dose Modification

Lipid Intolerance

If lipid intolerance develops, defined as serum triglyceride levels > 200 mg/dL, the following will be considered prior to reducing the dose:

- a) If the level was obtained while the patient was receiving a continuous 24-hour infusion of Omegaven®, the total dose should be infused over 20 hours, and a repeat serum triglyceride level obtained prior to resuming the infusion 4 hours later.

b) Other sources of lipid intolerance should be considered and addressed (drugs, renal disease)

If the triglycerides continue to remain high despite the aforementioned interventions, a dosage reduction of 25% of the current dose will be considered.

High Glucose Infusion Rate

Subjects with a high glucose infusion rate (GIR) will have a dose increase up to 1.5 grams/kg/day to allow for a reduction in PN calories from carbohydrates at the discretion of the Omegaven study team and the nutrition service.

Duration of Therapy

Patients will remain on Omegaven® until weaned from PN. Patients may continue monotherapy with Omegaven® as an additional source of calories after the dextrose/protein portion of PN is discontinued

In the event that a patient who has been listed for a liver or liver/intestinal transplant has an organ become available, the participation in this protocol will not preclude them from receiving the transplant.

Disruption of Therapy

In event that Omegaven® cannot be administered (i.e. loss of central venous catheter access, fluid restrictions, need to administer an incompatible medication/blood product), the infusion of Omegaven® may be interrupted and resumed when the conflicting situation is resolved. Some potential interventions that can be used include:

Situation	Possible Solution
Loss of central venous access	Administer via peripheral route
Fluid restriction	Consult with pharmacy to concentrate PN, medications to allow for administration

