Limited access, need to administer incompatible medications	Stop Omegaven® infusion, flush catheter with either NS or dextrose, administer incompatible medication, flush catheter, resume infusion; may be necessary to infuse Omegaven® over 8 -24 hours. Multiple syringes should be used so as to keep maximum hang time of Omegaven® source container less than 12 hours) Regardless of the infusion time, the infusion rate cannot exceed 0.15g/kg/hour.

Discontinuation of Therapy

Patients will continue to be followed by the Center for Advanced Intestinal Rehabilitation (CAIR) Program upon discontinuation of therapy with Omegaven® for a minimum of 2 months after the treatment is stopped.

Resumption of Therapy

For patients who have been off the protocol more than 1 year, in the event that the patient must receive intravenous fat emulsion, treatment with Omegaven® will resume only if the patient shows evidence of PN liver damage (elevations in direct bilirubin ≥ 2 or pathology findings consistent with cholestasis). Otherwise, the patient will be treated with conventional fat emulsion.

Soybean based Fat Emulsion (Intralipid® and/or Liposyn®)

Subjects in the Andorsky et al cohort received one of two commercially available intravenous fat emulsions (IFE), Liposyn® II or Intralipid®. IFE is provided as an oil-in-water emulsion derived from egg phospholipids, soybean or safflower oils and glycerol. Although three concentrations are commercially available (10, 20, 30%) only the 10 and 20% concentrations have been approved for use in children. Both Liposyn® II and Intralipid® contain soybean oils. Table 1 summarizes the composition of both products.

Details of IFE Administration

Regardless of the product used, doses less than 96 ml/day were repacked into syringes to allow for administration via syringe pump. Doses greater than 96ml/day were dispensed in the original manufacturer's container. If patients were discharged home on either IFE, all doses were administered from the original manufacturer's container.

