Generally, primary safety analyses will be based on time from baseline or 30 days after baseline until two months after patients first reached direct bilirubin levels $< 2\text{mg/dL}$. Baseline will be defined as information collected at the date that treatment starts for Omegaven[®] patients and on the date that patient reached bilirubin levels > 2 for soybean oil fat emulsion patients. Information on mortality and transplant will be collected during the whole treatment with Omegaven[®] and during the whole period for which we have data available in the Andorsky et al. dataset. Primary efficacy analysis will include time from baseline until the patient normalizes bilirubin (presents three consecutive direct bilirubin $\leq 2\text{ mg/dL}$ or a direct bilirubin $\leq 2\text{ mg/dL}$ and weaned from TPN). With exploratory purpose, we will also describe the curve of the several markers for the entire period that Andorsky et al. recorded data.

Outcome/Endpoints

1. Treatment safety

Our primary outcome for treatment safety will be based on patient's essential fatty acid profile. We will compare patients before treatment with Omegaven[®] started and after treatment started (one month after treatment started until treatment stopped) with respect to the frequency with which triene/tetraene ratio > 0.2 at any time. We will also compare the occurrence any event of of hypertriglyceridemia (serum triglyceride $> 400\text{mg/dL}$) between Omegaven[®] and soybean oil fat emulsions. Primary analyses for these and all other safety outcomes will be based on a follow-up time for Omegaven[®] and soybean oil fat emulsions starting 30 days after baseline, i.e., 30 days after treatment started for Omegaven[®] patients and 2 months after the first direct bilirubin level $< 2\text{ mg/dL}$ was recorded. We will also explore comparisons including the time from baseline until the end of follow-up period.

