Additional comparisons across treatment periods for subjects receiving Omegaven® will be aimed to assess occurrence of spontaneous bleeding (e.g., unexplained bruising, oozing from gums/incision sites), and maximum triene/tetraene ratio, minimum platelets, and maximum international normalized ratio (INR), trends in pre-albumin (age standardized levels). We will also explore trends in coagulopathies based on curves of platelets, prothrombin time (PT), partial thromboplastin time (PTT) over time, and INR. We will also describe the rate with which INR ratios were > 2 (number of days/follow-up time), as a marker of coagulopathies.

Additional comparisons between Omegaven® and soybean oil fat emulsion groups will be performed with regards to rate in which albumin is > 3 g/dL, maximum triglyceride level, rate of blood stream infections (number of positive blood cultures/follow-up-time under PN after baseline), rate of central venous catheter (CVC) infections (number of CVC infections/follow-up time and number of gram positive CVC infections/follow-up time), and occurrence of anaphylactic reactions after baseline.

Nutritional outcomes between Omegaven® and soybean oil fat emulsion groups that will be compared include changes in weight- and height-for-age Z-scores from baseline to 10% PN or cessation of PN..

We will describe trends over time for all outcomes associated with fatty acid profiles (including triene/tetraene ratios, triglycerides, total omega-6 fatty acids, total omega-3 fatty acids, total saturated, total monounsaturated, and total polysaturated fatty acids). Specific fatty acids such as arachidonic, palmoleic, palmitic, oleic, stearic, and linoleic fatty acids will also be evaluated and described. Also, for exploratory purposes, we will compare the trend in weight- and height-for-age Z-scores between both groups.

2. Omegaven®

3. The patient will complete treatment with Omegaven® in this study when he/she is completely off PN, develops a contraindication for further use, or the patient/family requests to be removed from the study.

f. Data Collection Methods, Assessments and Schedule

Omega-3 Fat Emulsion (Omegaven™)

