Analysis of Baseline Characteristics

For statistical purposes, baseline values will be defined as the last measurement before starting to administer Omegaven® for patients, in the treatment group, and as the measurement taken when a patient first had a direct bilirubin level > 2 mg/dL recorded, in the historical control group. Descriptive statistics for all baseline relevant risk factors will be summarized for Omegaven® (omega-3 based fat emulsion) and historical control (soybean oil fat emulsion) groups. Associations between categorical predictors and Omegaven® vs. soybean oil fat emulsion groups will be tested through chi-square tests. Associations between continuous predictors and treatment groups will be studied through means (and standard deviations) and t-tests, or medians (and interquartile ranges) and Wilcoxon tests, when appropriate.

Analysis of Safety and Tolerability of Omegaven®

All primary safety and tolerability analyses will be based on descriptive statistics. In secondary analyses, we will also assess the statistical significance of differences. Some safety and tolerability outcomes will be measured only in the Omegaven® group. For those, we will compare results before starting PN with Omegaven® (while receiving PN with soybean oil fat emulsions) with after starting PN with Omegaven®. The period receiving Omegaven® will start to be counted 30 days after beginning PN with Omegaven® for the main analysis. Outcomes measured in the Omegaven® and soybean oil fat emulsion groups will be described separately for each of those groups for a period starting 30 days after baseline, i.e., 30 days after starting PN with Omegaven®, for the treatment group, and 30 days after bilirubin > 2 mg/dL, for the soybean oil fat emulsion group.

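### Catheter infection rates are divided by all follow-up time, including days off PN, so the group comparison can be distorted in either direction

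*Combined protocol and SAP*

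**What the plan says.** Under Treatment safety, in the definition of primary and secondary outcomes (part e), two kinds of infection rate are defined in one sentence. Bloodstream infection is the "number of positive blood cultures/follow-up-time under PN after baseline". Line infection is the "rate of central venous catheter (CVC) infections (number of CVC infections/follow-up time and number of gram positive CVC infections/follow-up time", with no restriction to time on PN or time with a line.

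The introduction to part e runs the main safety analyses "until two months after patients first reached direct bilirubin levels" below 2 mg/dL. Section 5c (Data Analysis Plan) describes outcomes measured in both groups "for a period starting 30 days after baseline". It lists the line infection rates again without a denominator and summarises outcomes over each subject's follow-up.

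Follow-up can run past weaning in both groups. The design section follows historical controls until two months after three consecutive low bilirubin values, or after one low value "and were weaned from PN died, or underwent a liver transplant". Omegaven patients are followed "for a minimum of 2 months after the treatment is stopped". Leaving PN does not always end intravenous infusion: "Patients may continue monotherapy with Omegaven® as an additional source of calories after the dextrose/protein portion of PN is discontinued" (Duration of Therapy).

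**The concern.** A CVC infection needs a catheter. Days without one add to the denominator and cannot add to the numerator. The plan limits the bloodstream rate to PN time but leaves the more catheter-specific rates unrestricted. Two groups with the same risk per line-day will show different CVC rates whenever different shares of their windows are spent without a line.

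Section 5c lists line infection rates among the primary safety outcomes measured in both groups, and hypothesis 2.3 predicts fewer infections on Omegaven. The limitations section uses line infections as its example of an outcome open to historical-control bias and expects opposing biases to offset each other. It does not consider this one.

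**Working it through.** The documents give no infection rate, catheter-day count, or weaning or line-removal time, so there is no plan figure to reproduce. The check asks how far the stated denominator can move the rate ratio when the truth is 1.00.

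**From the documents.** The window starts 30 days after baseline (section 5c) and ends two months, taken as 60 days, after normalisation (part e).

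**Assumed.** The infection rate per PN-day, λ, is the same in both groups. Risk is zero off PN. The day of normalisation (N) and day of weaning (W), counted from baseline, are illustrative.

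**Formulas**

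- Window length = (N + 60) − 30
- PN days in window = min(W, N + 60) − 30
- Share = PN days ÷ window length
- Observed rate = λ × share
- Apparent ratio, Omegaven to control = Omegaven share ÷ control share (λ cancels)

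| Pattern | Omegaven N/W | Control N/W | Omegaven share | Control share | Ratio |
|---|---|---|---|---|---|
| Weaning at normalisation | 90/90 | 150/150 | 60/120 = 0.50 | 120/180 = 0.67 | 0.75 |
| Weaning at normalisation | 90/90 | 270/270 | 60/120 = 0.50 | 240/300 = 0.80 | 0.63 |
| Weaning at normalisation | 60/60 | 365/365 | 30/90 = 0.33 | 335/395 = 0.85 | 0.39 |
| Both on PN throughout the window | 90/400 | 270/400 | 120/120 = 1.00 | 300/300 = 1.00 | 1.00 |
| Omegaven normalises while on PN | 90/150 | 270/270 | 120/120 = 1.00 | 240/300 = 0.80 | 1.25 |
| Controls normalise after weaning | 90/120 | 300/200 | 90/120 = 0.75 | 170/330 = 0.52 | 1.46 |

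A simpler version of the first pattern ignores the 30-day start. With 100 against 200 at-risk days, each followed by 60 days without a line, the shares are 100/160 = 0.625 and 200/260 = 0.769, a ratio of 0.81.

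Starting the window at baseline changes the size but not the pattern: the 90/90 against 270/270 case gives (90/150) ÷ (270/330) = 0.73, and the last row gives (120/150) ÷ (200/360) = 1.44.

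**Direction.** N and W in each group were each set to 60, 90, 120, 180, 240, 300 and 365 days, keeping the 441 combinations in which one group both normalised and weaned sooner. That group's apparent rate was lower in 264, higher in 96 and equal in 81. These are counts of grid points, not probabilities.

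**With time at risk as denominator** the ratio is λ ÷ λ = 1.00 in every case, by construction.

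**The case against.** There is a fair case that this matters less than it seems.

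- The protocol expects Omegaven to let children remain on adequate PN, and its laboratory schedule covers patients on Omegaven with direct bilirubin at or below 2 mg/dL. Hypothesis 2.1 expects bilirubin to stay high in controls. Those expectations fit the patterns with no distortion, or distortion against Omegaven, at least as well as the pattern that flatters it.
- Part e names the essential fatty acid profile as the primary safety outcome and places CVC rates among additional comparisons. Section 5c makes the primary safety analysis descriptive and between-group testing exploratory. Infection rates are also compared by log-rank and Cox models.
- The author may have meant the PN restriction to carry through the sentence.
- The stated control data are an existing spreadsheet abstracted at two-week intervals, and line dates are not mentioned.

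The first point stands and rules out a claim about direction. The second lowers the weight, but a descriptive rate with a mismatched denominator still misleads, and section 5c does not say how the log-rank and Cox analyses treat time off PN. The third is possible, but the text does not say so and section 5c does not restore the restriction. The fourth limits which denominator is feasible; it does not justify using all follow-up time.

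**Conclusion.** The CVC denominator is broader than the time at risk and does not match the bloodstream rate defined beside it. It can produce a false group difference, or hide a real one. Under the assumed times the apparent ratio runs from 0.39 to 1.46 when the truth is 1.00. Zero risk off PN is also an assumption: if lines stay in and carry the same risk throughout the window, there is no distortion.

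A reader might infer that the rule builds in an advantage for the group that recovers sooner, and so for Omegaven. The documents do not support that. The diluting quantity is off-PN time inside the window, not a fixed 60 days. It is zero if PN continues for two months past normalisation, and exceeds 60 days if weaning comes first. Nor do the documents show that many patients are weaned and without a line by the end of the window: they give no such dates and allow Omegaven to continue intravenously after the rest of PN stops.

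Because the analysis is descriptive and the correction simple, this is a cheap improvement rather than a major flaw.

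**What to change.** In part e and section 5c, replace follow-up time for both CVC rates with time at risk, defined the same way in both groups: days on any intravenous nutrition or lipid within the safety window, including Omegaven alone after the rest of PN stops. Count only infections arising in that time. Use catheter-days instead only if line insertion and removal dates can be obtained for both groups. Keep the all-follow-up rate as a sensitivity analysis, and apply the same at-risk time in the log-rank and Cox infection analyses. The bloodstream denominator need not be made identical, since a positive culture need not come from a catheter.

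The cost is mainly wording, because PN time is already needed for the bloodstream rate. The downside is that PN or lipid days are only a proxy for catheter-days. A line may outlast infusion, Omegaven may be given peripherally, and the historical data resolve time only to two-week intervals. The plan should state these limits.
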